#### Exposure adjusted incidence rate (EAIR) and exposure adjusted 10.2.2 event rate (EAER)

The EAIR is defined as the number of subjects  $(n_{AE})$  with a specific AE adjusted for the sug, exposure and will be scaled to 100 patient-years:

$$EAIR = 100 * \frac{n_{AE}}{\sum_{i=1}^{n_{AE}} T_{Exp,i} + \sum_{j=1}^{n_{noAE}} T_{Risk,j}}$$
(39)

where  $T_{Exp,i}$  is a subject's exposure time in years up to the first occurrence of the AE of interest (equation [36] in years) at the level of coding evaluated, nnoAE the number of subjects without the specific AE and  $T_{Risk,i}$  the total time at risk scaled to 100 patient-years (Section 10.1).

If a subject has multiple events at the level of coding evaluated, the time of exposure is calculated to the first occurrence of the AE of interest. If a subject has no events, the total time at risk (Section 10.1) in years is used. As indicated above, exposure-adjusted incidence rates will only be calculated for the overall treatment period. These presentations do not include AEs that occur under Placebo treatment. Therefore, a subject's exposure time will only start at the first dose of bimekizumab in the Dose-Blind Period for subjects randomized to Placebo at Baseline. Also, for subject's randomized to bimekizumab 16mg or 64mg at Baseline, exposure time will only be considered from the start of Dose-Blind Period, when presenting AEs for the bimekizumab 160mg, or bimekizumab 320mg groups. All exposure time on any bimekizumab dose is considered for the all bimekizumab column.

Exact Poisson 95% confidence intervals for incidence rates are calculated using the relationship . This document ca between the Poisson and the Chi-square distribution (Ulm, 1990; Fay and Feuer, 1997):

$$LCL = \frac{\chi^2_{2n_{AE},\underline{\alpha}}}{2} \tag{40}$$

$$UCL = \frac{\chi_{2(n_{AE}+1),1-\alpha/2}^{2}}{2}$$
(41)

(43)

$$CI_{Lower} = 100 * \frac{LCL}{\sum_{i=1}^{n_{AE}} T_{Exp,i} + \sum_{j=1}^{n_{noAE}} T_{Risk,j}}$$
(42)

$$CI_{Upper} = 100 * \frac{UCL}{\sum_{i=1}^{n_{AE}} T_{Exp,i} + \sum_{j=1}^{n_{noAE}} T_{Risk,j}}$$

where  $n_{AE}$  is the number of subjects with a specific AE for the incidence rate of interest and is the basis for the number of the degrees of freedom for the chi-square quantile for the upper tail probability  $\chi^2$ ,  $T_{Exp,i}$  is a subject's exposure time in years up to the first occurrence of the AE of interest (equation [36] in years) at the level of coding evaluated,  $n_{noAE}$  the number of subjects without the specific AE and  $T_{Risk,j}$  the total time at risk scaled to 100 patient-years (Section 10.1).

The EAER will be the number of AEs including repeat occurrences in individual subjects divided by the total time at risk scaled to 100 patient-years and calculated using:

$$EAER = 100 * \frac{N_{AE}}{\sum_{j=1}^{n_{AE}} T_{Risk,j}}$$
(44)

where  $N_{AE}$  is the total number of AEs,  $T_{Risk,j}$  is a subject's total time at risk in years and  $n_{AII}$  the number of subjects.

No confidence interval will be computed for EAER.

## 10.2.3 AE of Special Interest and AE of Special Monitoring

AE of special interest is any AE which meets the Hy's Law criteria, defined as  $\geq$ 3x upper limit of normal (ULN) alanine aminotransferase (ALT) or aspartate aminotransferase (AST) with coexisting  $\geq$ 2xULN total bilirubin in the absence of  $\geq$ 2xULN alkaline phosphatase (ALP), with no alternative explanation for the biochemical abnormality.

AE of special monitoring for this study include:

- Infections (serious, opportunistic, fungal and TB)
- Malignancies, including lymphoma
- Major cardiovascular events
- Neutropenia

• Neuropsychiatric events (in particular depression and suicide)

- Inflammatory bowel disease
- Anaphylactic reaction
- Hepatic events

For the definitions of AE of special monitoring the Bimekizumab Safety Topics of Interest (Version date 19Feb2018) will be used.

The incidence of TEAEs of special monitoring will be summarized by MedDRA system organ

- regardless of the High Level Term (HLT) it codes to.
- The second overall incidence row will summarize "Any malignancy (including unspecified, excluding non-melanomic skin cancers)" and this row will summarize the incidence of AEs flagged for inclusion in the table, excluding those which code to an HLT of "skin neoplasms" malignant and unspecified (excl melanoma)".

The output table for the search criteria SMQ="Malignant tumours (SMQ)" will include two different overall rows:

- The first overall incidence row will summarize "Any malignancies" and this row will ۲ summarize the incidence of all AEs flagged for inclusion in the table, regardless of the High Level Term (HLT) it codes to.
- The second overall incidence row will summarize "Any malignancy (excluding nonmelanomic skin cancers)" and this row will summarize the incidence of AEs flagged for inclusion in the table, excluding those which code to an HLT of "skin neoplasms malignant and unspecified (excl melanoma)"

The output table for Anaphylactic reaction will include three different overall rows:

- The first row within the body of the table will be labeled "Any hypersensitivity/anaphylactic • reaction" and will represent the overall incidence of subjects who reported at least one hypersensitivity reaction or at least one anaphylactic reaction.
- The second row within the body of the table will be labeled "Any hypersensitivity reaction" and will represent the overall incidence of subjects who reported at least one hypersensitivity reaction.
- The third row within the body of the table will be labeled "Any anaphylactic reaction" and will represent the overall incidence of subjects who reported at least one anaphylactic reaction.

## **Clinical laboratory evaluations**

his docurr The routine clinical laboratory evaluations specified in Table 10-1 and will be summarized. If any additional analytes are also recorded then these will be listed only.

Different summary tables for hematology and biochemistry variables will be provided, based on data from scheduled visits: observed values and change from Baseline, shift from Baseline to

maximum post-Baseline value (in Double-Blind Period), shift from Baseline to maximum post-Baseline value (in Dose-Blind Period), shift from Baseline to minimum post-Baseline value (in Double-Blind Period), shift from Baseline to minimum post-Baseline value (in Dose-Blind

Linu of treatment (in Double-Blind Period) will be defined as the last visit in the Double-Blind Period or the early termination assessment depending if the subject discontinued in the Double-Blind Blind Period.

End of treatment (in Dose-Blind Period) will be defined as the Week 48 visit or the early of termination assessment depending if the subject discontinue 1

In addition, number of subjects who meet the Hy's Law criteria (Section 10.2) will be described using frequencies.

All laboratory data will be listed by treatment, subject and visit including changes from Baseline for numeric variables, flags for measurements outside the normal ranges, the relative study day, a flag for whether the test was not done and a flag for whether the subject was fasting.

Additional listings will be presented for Hepatitis B and C, human immunodeficiency virus (HIV), genomic proteomic/metabolomics, and genetic/epigenetic tests. CRP and hs-CRP will be tabulated and listed separately in the efficacy section

Hematology	Biochemistry	Urinalysis
Basophils	Biochemistry C Hot Calcium	Bacteria
Eosinophils	Chloride	Crystals
Lymphocytes	Magnesium	Glucose
Monocytes	Potassium	pH
Neutrophils	Sodium	RBC
Hematocrit	Glucose	WBC
Hemoglobin	BUN	Urine dipstick for pregnancy testing
MCH god	Creatinine	
MCHC C	AST	
MCV ot	ALT	
Platelet count	ALP	
RBC count	GGT	
WBC count	Total bilirubin	
WBC count	LDH	
	Uric acid	
	Total cholesterol	

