#### 3.1 General presentation of summaries and analyses

lations thereof. All computations and generation of outputs will be performed using SAS® Version 9.3 or later. All tables and listing will use Courier New font size 9.

All original and derived variables will be listed and described using summary statistics (number of observations [n], mean, standard deviation [SD], median, minimum and maximum, unless otherwise stated) or frequency counts (number of subjects [N] and percentages). For multiple post-Baseline assessments at a specific visit, the first non-missing measurement will be used for summary statistics or frequency counts.

Descriptive statistics will be displayed to provide an overview of the study results. For categorical variables, the number and percentage of subjects in each category will be presented. The denominator for percentages will be based on the number of subjects appropriate for the purpose of analysis. Unless otherwise noted, all percentages will be displayed to 1 decimal place. No percentage will be displayed for zero counts, and no decimal will be presented when the percentage is 100%. For continuous variables, descriptive statistics will include number of subjects with available measurements (n), mean, SD, median, minimum, and maximum.

Decimal places for descriptive statistics will always apply the following rules:

- "n" will be an integer.
- Mean, SD, and median will use 1 additional decimal place compared to the original data.
- Coefficient of variance (CV [%]) will be presented with 1 decimal place.
- Minimum and maximum will have the same number of decimal places as the original value.

Statistical tests of efficacy variables will be presented as 2-sided p-values rounded to 3 decimal places. P-values less than 0.001 will be presented as "<0.001" and p-values greater than 0.999 will be presented as \$\$0.999". Statistical comparisons will be performed by two-sided statistical tests at the 0.050 level of significance.

The SAS output for Cochran-Mantel-Haenszel test, logistics regression, and analysis of covariance (ANCOVA), as well as multiple imputation (MI) will be provided as a separate PDF document in addition to TFLs. The SAS output will be included in the 'Documentation of Statistical Methods' section of the clinical study report.

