In the Double-Blind Period the order of treatment groups to be presented in tables from left to right will be Placebo, BKZ16mg, BKZ64mg, BKZ160mg, and BKZ320mg, where BKZ is the abbreviation for bimekizumab. The general principle is to go from the lowest to highest dose when moving from left to right. Tables may also include columns for all subjects or all subjects on bimekizumab. An overview of the treatment group assignment is available in Table 12–2.

hisdocu

Selected tables which are specified in the TFL shells will only use data from the Dose-Blind Period. For listings and the selected tables, the label and order of treatment groups will be presented as follows: Placebo-BKZ160mg, Placebo-BKZ320mg, BKZ16mg-BKZ160mg,

A complete set of data listings containing all documented data and all derived data (eg, changed in the from Baseline) will be generated. including timing relative to dosing if applicable). For listings including nonrandomized subjects, the nonrandomized subjects will be shown first in the listing, ordered by subject number. All listings will include repeat and unscheduled measurements; such measurements will appear in chronological order together with the scheduled visits, ie, a repeated measurement will appear directly after the visit and time relative to dosing for which the repeat measurement was performed. In all the listings dates will be presented in the format "YYY-MM-DD" and times will be presented in 24h clock format as "hh:mm".

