## Table 10–1: Laboratory measurements

ALP=alkaline phosphatase; ALT=alanine aminotransferase; AST=aspartate aminotransferase; BUN=bloothrea nitrogen; CRP=C-reactive protein; GGT=gamma glutamyltransferase; hs-CRP=high sensitivity C-reactive protein; LDH=lactate dehydrogenase; MCH=mean corpuscular hemoglobin; MCHC=mean corpuscular hemoglobin concentration; MCV=mean corpuscular volume; RBC=red blood cell; SFU=Safety Follow-up; WBC=white blood cell

a A serum pregnancy test will be performed at Screening for all women of childbearing potential. This recommendation also applies to women of childbearing potential with infrequent or irregular menstrual cycles and women during menopause. Natural menopause is recognized to have occurred after 12 consecutive months of amenorrhea, for which there is no other obvious pathological or physiological cause (International Menopause Society, 2015). A urine pregnancy test is also required at the Baseline, Week 48, ET, and at SFU visits. A urine pregnancy test will also be performed at any study visit where there has been a delay in menses. This recommendation also applies to women of childbearing potential with infrequent or irregular menstrual cycles. Pregnancy test results must be negative prior to administering IMP.

b Both CRP and hs-CRP will be tested at specified visits per Protocol Table 5.1.

Markedly abnormal values for biochemistry and hematology will be defined as laboratory values graded 3 or 4 according to the Rheumatology Common Toxicity Criteria (RCTC). Definitions of the markedly abnormal values are given in Table 10–2 and Table 10–3 and are based on the RCTC units. All units in the tables below will be converted to the standard international units based on Clinical Data Interchange Standards Consortium (CDISC) standards.

Values that are below the lower limit of the reference range will be flagged as "L" (low) and values that are above the upper limit of the reference range will be flagged as "H" (high) and listed as well.

For tables where data are summarized by visit, unscheduled and repeat visits will not be summarized, but these data will be included in listings. In the case where laboratory values are below the lower limit of quantification, then these will be set to the midpoint between 0 and the lower limit of quantification for the purpose of summarizing the data.

Table  $10-2^{\circ}$  Definitions of Markedly Abnormal Biochemistry Values

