## 10.4 Potential drug-induced liver injury (PDILI) assessment

All potential drug-induced liver injury (PDILI) events require immediate action, testing, and monitoring. The measurements and additional information required for the assessment of PDILI events when there is a reasonable possibility that they may have been caused by the IMP are included but not limited to those listed in Table 10–4 (additional information) and Table 10–5 (laboratory measurements).

**PDILI** laboratory results and additional PDILI information will only be listed by treatment group and subject. If specific PDILI information collected separately is matching to the entries in the standard eCRF pages collected for all subjects, the specific PDILI information will be added to the corresponding listing for the standard eCRF information (eg, lifestyle information is collected for all study subjects, the additional PDILI information for alcohol and illicit drug use will be included in the listings for lifestyle). For information collected on top (eg, family history of PDILI) a new listing will be generated.

ts there of

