### Has been changed to

. . .

variations thereof. Different summary tables for hematology and biochemistry variables will be provided, based on data from scheduled visits: observed values and change from Baseline, shift from Baseline to maximum post-Baseline value (in Double-Blind Period), shift from Baseline to maximum post-Baseline value (in Dose-Blind Period), shift from Baseline to minimum post-Baseline value (in Double-Blind Period), shift from Baseline to minimum post-Baseline value (in Dose-Blind Period), shift from Baseline to end of treatment (in Double-Blind Period), shift from Baseline to end of treatment (in Dose-Blind Period), and markedly abnormal laboratory data.

End of treatment (in Double-Blind Period) will be defined as the last visit in the Double-Blind Period or the early termination assessment depending if the subject discontinued in the Double-Blind Period.

End of treatment (in Dose-Blind Period) will be defined as the Week 48 visit or the early termination assessment depending if the subject discontinued early or not.

... Table 10-5 updated to align with Table 12-4 from the Protocol Amendment 2. This document cannot be used to support any many

The formation of the seaf of t

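### The worst-value shift tables and the markedly abnormal laboratory table draw on scheduled visits only, so a Grade 3/4 value seen only at an unscheduled, repeat or liver work-up draw is left out of them

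*SAP*

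**What the plan says.** Section 10.3 introduces the hematology and biochemistry tables with a restriction to "data from scheduled visits: observed values and change from Baseline, shift from Baseline to" and then goes on to the worst-value tables: "maximum post-Baseline value (in Double-Blind Period), shift from Baseline to maximum post" and the matching minimum tables for each period. The end of this list is lost from Section 10.3 in the text available. The replacement wording in Section 13.5.2 (Amendment 5) supplies it: "end of treatment (in Dose-Blind Period), and markedly abnormal laboratory data". Markedly abnormal means "graded 3 or 4 according to the Rheumatology Common Toxicity Criteria (RCTC"), with the limits in Tables 10-2 and 10-3.

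Three other provisions bear on which results are used:

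- Later in Section 10.3, on unscheduled and repeat visits: "For tables where data are summarized by visit, unscheduled and repeat visits will not be" summarized, although they are kept in listings.
- Section 3.1, for several "post-Baseline assessments at a specific visit, the first non-missing measurement will be used for" summary statistics and frequency counts.
- Section 10.4, on the liver work-up: "laboratory results and additional PDILI information will only be listed by treatment group" and subject.

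Section 3.1 also says of listings: "All listings will include repeat and unscheduled measurements".

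**The concern.** For a mean by visit, leaving out unscheduled draws is ordinary practice, because it keeps the time points comparable. A shift to the maximum post-Baseline value, or a count of subjects with a Grade 3/4 result, asks a different question: how bad did this subject's result become during the period? Computed from scheduled visits alone, such a table does not report what its title says.

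Change in laboratory variables is a listed safety variable, and neutropenia and hepatic events are under special monitoring (Section 10.2.3). ALT and AST are among the PDILI laboratory measurements (Table 10-5), so the liver results that are listed only include the analytes for which the peak matters most. At stake is whether the tabulated worst values and Grade 3/4 incidences by dose are complete.

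**Working it through.** The SAP states no figure on this point, so there is none to reproduce. The check is mainly of the text.

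**1. Which tables are restricted.** The reference to scheduled visits stands before the colon that opens the list, so it governs every item: observed values and change, maximum and minimum shifts in each period, end-of-treatment shifts and, from Section 13.5.2, the markedly abnormal table.

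**2. Whether another rule restores the excluded results.**

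| Source of result | Provision | In the worst-value and markedly abnormal tables? |
|---|---|---|
| Unscheduled visit | 10.3, scheduled-visit basis | No |
| Repeat at a scheduled visit | 3.1, first non-missing value | No |
| PDILI draw | 10.4, listed only | No |
| Early termination visit | 3.5, mapped to a scheduled visit | Yes |

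The by-visit sentence in Section 10.3 does not restore anything. It says what by-visit tables leave out, not what the other tables take in.

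**3. Direction.** Let S be a subject's results used under the plan and A all of that subject's post-Baseline results in the period, so that S is a subset of A. Then:

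- max(S) ≤ max(A);
- min(S) ≥ min(A);
- the number of subjects with a Grade 3/4 value in S ≤ the number with one in A.

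With the denominator held fixed, every difference is towards less abnormal. There is no difference for a subject whose worst result is already in S. A subject with a Grade 3/4 value in S is already counted as markedly abnormal, and a confirmatory repeat adds nothing to that count.

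**4. Size per subject.** The planned arm size is 57 (Section 2.4), and 1/57 = 1.75 percentage points for each subject omitted from a Double-Blind arm. For the Dose-Blind Period, suppose tables pool by dose received and nobody drops out. The three re-randomized arms give 3 × 57 = 171 subjects, about 85 to each dose, so about 57 + 85 = 142 per dose and 1/142 = 0.7 points per subject.

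The number of such subjects cannot be derived. The SAP does not give the laboratory schedule or the frequency of unscheduled draws.

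**The case against.** **The values are not lost.** A reader might infer that an unscheduled Grade 3/4 result appears in no summary table at all. The SAP does not support that. Section 10.2 counts an abnormal laboratory finding as a possible adverse event, and haematopoietic cytopenia and hepatic events have their own incidence tables. The Hy's Law count stands outside the restricted list and carries no stated visit limit. All laboratory results are listed, with flags for values outside the normal range. This limits the consequence, but capture elsewhere depends on the value being reported as an event or meeting Hy's Law. It does not put the value into the tables whose titles promise it.

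**The two sentences do not contradict each other.** One restricts all the tables and the other excludes unscheduled and repeat visits from by-visit tables, so both can be followed at once. The amendment history also suggests a deliberate choice: Amendment 4 inserted the scheduled-visit phrase and Amendment 5 kept it. That stands. What remains is a difference of scope: the narrower sentence adds nothing for these tables if the broader one governs, and a programmer could wonder whether only by-visit tables were meant.

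**Dose selection at Week 12 is not affected.** Section 4.3.1.1 places Amendment 3 after the Week 12 interim, and the restriction came only with Amendment 4. A reader might infer that the analysis used to choose doses was run under it; the sequence of amendments shows that it was not.

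**Frequency is not shown.** PDILI testing follows a signal already detected, often perhaps at a scheduled draw that already counts. That is fair. The point rests on what the tables claim to report and on the direction of the error, not on an estimated rate.

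**Conclusion.** The point holds for the maximum and minimum shift tables and the markedly abnormal table. As written, they leave out unscheduled and PDILI results and, through Section 3.1, repeats at a scheduled visit, so they can only understate worst values and Grade 3/4 counts. The effect is confined to subjects whose worst or only qualifying value came from such a draw: 1.75 points each in a Double-Blind arm of 57, with the number of subjects unknown. It is not an internal contradiction, a loss of data or a flaw in the Week 12 dose selection.

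The conclusion assumes that the list in Section 10.3 ends as Section 13.5.2 shows. Without that, it would still hold for the maximum and minimum shift tables, which are in the body text. The change is worth making because the results are already collected and listed.

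**What to change.** In Section 10.3, limit the scheduled-visit basis to the observed-value, change-from-Baseline and end-of-treatment tables. State that the maximum and minimum shift tables and the markedly abnormal table use every post-Baseline result in the period, including unscheduled, repeat and PDILI draws, and that for these tables this overrides the first-non-missing rule of Section 3.1. Word the later sentence on unscheduled and repeat visits to the same scope. It would also help to state the data basis of the Hy's Law count.

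The cost is a sentence or two in the SAP and a change in record selection for the affected table programs, with PDILI results brought in and each result assigned to a period by its date. Reported incidences of abnormal values may be slightly higher. No new data are needed.
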